### **6.5.6 HIV and Hepatitis B and C Testing**

Patients with a known history of HIV or who are HIV antibody positive should be tested for HIV ribonucleic acid (RNA) during screening. No further testing beyond screening is necessary if PCR results are negative, except if clinically indicated.

Patients who are anti-HBc positive, or have a known history of HBV, should have quantitative PCR testing for HBV DNA performed during screening and every 3 months thereafter.

Monitoring (every 3 months) should continue until 12 months after last dose of acalabrutinib.

Any patient with a rising viral load (above lower limit of detection) should discontinue acalabrutinib and have antiviral therapy instituted and a consultation with a physician with expertise in managing hepatitis B. As IVIG may cause false positive hepatitis serology, monthly PCR testing is not required in patients who are currently receiving or received prophylactic IVIG within 3 months before study enrollment and have a documented negative anti-HBc test before the initiation of IVIG therapy. PCR testing should be performed when clinically indicated (e.g., in the setting of rising transaminase levels).

Patients with a known history of HCV or who are hepatitis C antibody positive should be tested for HCV RNA during screening. No further testing beyond screening is necessary if PCR results are negative, except if clinically indicated.

### **6.5.7 Clonality (ID) Sample**

The clonoSEQ Clonality (ID) Test determines the clonal diversity of a sample and can also be used to identify the trackable immune receptor sequence(s) of a lymphoid clone. Please ensure slide box and individual slides are each labeled with **Subject ID and Collection Date**.

Details of sample collection, processing, shipping, and storage will be described in the laboratory manual.

### **6.5.8 Tracking (MRD) Sample**

The clonoSEQ Tracking (MRD) Test uses follow-up samples for the purposes of following the immune receptor sequence(s) identified by the clonoSEQ Clonality (ID) Test. Please ensure individual samples are labeled with **Subject ID and Collection Date**.

Details of sample collection, processing, shipping, and storage will be described in the laboratory manual.

### **6.5.9 Fresh Lymphoma Biopsy Sample**

When feasible, collection of a lymphoma biopsy at relapse is encouraged, but will not be considered a protocol deviation if the patient withdraws consent. This sample will be used to investigate changes in pathway signaling and potential mechanisms of resistance (i.e., genetic alterations or evidence of alternative pathway activation). For this reason, a relapse lymphoma biopsy is encouraged in patients who achieve an objective response to the study drug, but later relapse.

All fresh lymphoma biopsies will be formalin-fixed and paraffin-embedded slides. Failure to obtain a sufficient lymphoma sample after making best efforts to biopsy the lymphoma will not be considered a protocol deviation.

If additional lymphoma molecular profiling is required to further understand any response to the study drug, the Sponsor may request a sample of the most recent lymphoma biopsy for additional research.

The results of this exploratory research will be reported separately and will not form part of the clinical study report (CSR).

Details of sample collection, processing, shipping, and storage will be described in the laboratory manual.

### **6.5.10 Response and Activity Assessments**

See Section 6.5.12, Section 6.5.13 and Section 9.

### **6.5.11 Adverse Event Assessments**

Information regarding the occurrence of AEs, including infections, will be collected from the time the patient signs the ICF throughout their participation in the study, including a period of 30 days after the last dose of study drug. Adverse event severity will be determined using the CTCAE Version 5.0 grading scale. See Section 11 for more details.

### **6.5.12 Prior and Concomitant Medications**

All concomitant medications are to be collected and recorded from the time the patient signs the ICF throughout the patient's participation in the study.

### **6.5.13 Minimal Residual Disease Assessment**

Adaptive Biotechnologies will use the clonoSEQ® assay to investigate potential changes in MRD status (MRD+ to MRD) in response to acalabrutinib therapy. Bone marrow aspirate will be collected at Day +100 (Screening #2) and 1 year post-BMT (~Cycle 10 Day 1). Blood samples will be collected at Day +100 (Screening #2), 6 months (~Cycle 4 Day 1), 1 year (~Cycle 10 Day 1) and 2 years post-BMT (~Cycle 22 Day 1). For time points where both blood and BM are tested, if a patient has an MRD+ result from either sample source (blood or BM), then the patient is considered MRD+. If the limit of detection and the limit of quantitation are not met and the MRD results are indeterminate, indicating an inadequate sample was used, then the patient will have a follow-up test performed at the discretion of the Investigator (see Section 9.3).

Next-generation sequencing (NGS) will be conducted on all bone marrow and blood samples.

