### **9.3 Minimal Residual Disease**

Minimal residual disease (MRD) is defined as the minimal traceable persistence of lymphoma after treatment with acalabrutinib. The clonoSEQ® assay, developed by Adaptive Biotechnologies, is an NGS-based immunosequencing platform that will be used for the detection, quantification and analysis of MRD. The assay uses multiplex PCR, high throughput sequencing and a proprietary algorithm for evaluating lymphoid clonal distribution and expansions in genomic DNA. MRD positive or negative results will be determined by detection

of residual clonal cells (with assay sensitivity of  $10^{-6}$ ) per Adaptive Technologies' reporting methods.

An MRD status will be defined as all results from whole blood and BM that meet the assay testing requirements and are negative for the presence of residual clonal cells. An MRD+ status will be defined as all results from whole blood or BM that are positive for residual clonal cells per Adaptive Biotechnologies' reporting methods. In addition to MRD positivity or negativity, MRD level will be captured by recording the number of residual clonal cells detected.

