#### **10.4.2 Efficacy Analysis**

All efficacy analyses will be performed using the Efficacy Analysis Set.

- PFS is defined as the time from Day 0 of BMT to objective radiological PD or death on study. PFS will be evaluated as Kaplan-Meier estimates of the percentage of subjects who receive at least one dose of study drug and who are alive and free of PD or relapse at 2 years post-BMT according to RECIL (Younes et al 2017). Data for subjects who are still alive and free from progression at the time of data cut-off date, are lost to follow-up, have discontinued the study, or have initiated a subsequent protocol therapy will be censored on last assessment (or, if no post-baseline tumor assessment, at the time of first dose plus 1 day). Approximate 95% CI for median duration of PFS will be computed using the formula proposed by Brookmeyer and Crowley.
- Minimal residual disease status will be examined by NGS on all bone marrow aspirate and blood samples collected up to 2 years post-BMT to determine the conversion rate from MRD+ to MRD while taking acalabrutinib, correlate MRD status with PFS, and identify mutations that correlate with disease relapse. An MRD status will be defined as all results from whole blood and BM that are negative for the presence of residual clonal cells (with assay sensitivity of 10^-6). An MRD+ status will be defined as all results from whole blood or BM that are positive for residual clonal cells per Adaptive Biotechnologies' reporting methods.

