- n. Patients with a known history of hepatitis C virus (HCV) or who are hepatitis C antibody positive should be tested for HCV RNA during screening. No further testing beyond screening is necessary if PCR results are negative, except if clinically indicated (see Section 6.5.6).
- o. If not obtained during Screening #1 (prior to BMT)
- p. Collect a fresh lymphoma biopsy at disease progression
- q. **MRD analysis with blood sample:** Collect a blood sample prior to beginning maintenance on Day +100 (Screening #2), 6 months (~Cycle 4 Day 1), 1 year (~Cycle 10 Day 1) and 2 years post-BMT (~Cycle 22 Day 1).
- r. **MRD analysis with bone marrow biopsy and aspirate:** Collect a bone marrow biopsy and aspirate prior to beginning maintenance on Day +100 (Screening #2) and at 1 year post-BMT (~Cycle 10 Day 1).
- s. CT/MRI/FDG-PET scans will be done post-BMT (Day 80-100), at 6 months, 12 months, 18 months and 24 months. Thereafter, scans will be done per institutional standard operating procedures.
- t. Record all AEs regardless of seriousness or relationship spanning from the first dose of acalabrutinib until 30 calendar days after discontinuation or completion of study drug.
- u. Coagulation testing will include PT/INR or aPTT.

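### MRD conversion at 6 and 24 months sets a blood-only result against a blood-or-marrow baseline, which can only push the rate up

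*Combined protocol and SAP*

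**What the plan says.** Section 2.2 makes conversion from MRD+ to MRD- during therapy, up to 2 years post-BMT, a secondary objective.

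Section 6.5.13 sets the samples. For marrow: "Bone marrow aspirate will be collected at Day +100 (Screening #2) and 1 year post-BMT (~Cycle 10 Day 1". For blood: "Blood samples will be collected at Day +100 (Screening #2), 6 months (~Cycle 4 Day 1), 1 year (~Cycle 10 Day 1", and again at 2 years. Appendix D agrees. Footnote r for marrow reads "Collect a bone marrow biopsy and aspirate prior to beginning maintenance on Day +100 (Screening #2) and at 1 year post-BMT", and footnote q for blood reads "Collect a blood sample prior to beginning maintenance on Day +100 (Screening #2), 6 months (~Cycle 4 Day 1), 1 year", followed by 2 years. The visit lists in Sections 6.4.2 to 6.4.4 match this: blood only in Cycles 2-6, blood and marrow in Cycles 7-12, blood only from Cycle 13.

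Section 6.5.13 also gives the rule for combining sources. It is limited to visits at which both are assayed: a patient with an MRD+ "result from either sample source (blood or BM), then the patient is considered" MRD+.

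For the analysis, Section 10.4.2 says that MRD "status will be examined by NGS on all bone marrow aspirate and blood samples collected up to 2 years post-BMT" to obtain the conversion rate. It adds that an MRD- "status will be defined as all results from whole blood and BM that are negative for the presence of residual clonal cells". Section 9.3 words it almost identically, with a condition on assay adequacy: MRD- "status will be defined as all results from whole blood and BM that meet the assay testing requirements" and are negative. Neither section says how a visit with blood alone is compared with a baseline built from two sources. Section 10.4 leaves the full description of the analysis to the Statistical Analysis Plan.

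**The concern.** A conversion rate is a before-and-after comparison, so the measurement should be the same before and after. Here the baseline is positive if either of two compartments is positive, while status at 6 and 24 months looks at one compartment only. A patient can then leave the MRD+ group because marrow was not sampled, with no change in disease.

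The 24-month visit is the end of therapy, where a reader will most want to know whether maintenance cleared residual disease. The protocol does not presume that blood and marrow agree: Section 2.3 makes their correlation an exploratory question. For imaging it already requires consistency. Under Section 6.5.14, a patient followed by MRI must have MRI at baseline and at every later evaluation. MRD has no matching requirement.

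**Working it through.** The plan states no conversion figure to reproduce, so the check sets the schedule beside the status rules.

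**Step 1. Sources by visit** (Section 6.5.13; Appendix D footnotes q and r). The last column follows a patient whose marrow is positive and whose blood is negative throughout, with blood-only visits scored on blood.

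| Visit | Blood | Marrow | Status rests on | This patient reads |
|---|---|---|---|---|
| Day +100 | yes | yes | either source | MRD+ |
| 6 months | yes | no | blood | MRD- |
| 12 months | yes | yes | either source | MRD+ |
| 24 months | yes | no | blood | MRD- |

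The disease never changes, yet the patient counts as converted at two of the three post-baseline visits. If conversion means MRD- at any time on therapy, the 6-month result alone is enough, and nothing in Section 10.4.2 lets the 12-month marrow reverse it.

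**Step 2. Direction.** Composite status is negative only if blood and marrow are both negative. Blood-only status is negative whenever blood is negative. Every composite negative is therefore also a blood-only negative, but not the reverse. Among patients who were composite MRD+ at Day +100, the rate from a blood-only visit is at least the composite rate at that visit, so the mismatch can add converters but never remove them.

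**Step 3. Size, by assumption only.** Let c be the true conversion rate in both compartments. Let f be the share of the remaining patients who were positive only in marrow at Day +100 and still are. Then

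apparent rate at a blood-only visit = c + (1 - c) × f.

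The documents give neither c nor f. The values below are assumed.

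| c | f = 0% | f = 10% | f = 40% |
|---|---|---|---|
| 0% | 0% | 10% | 40% |
| 20% | 20% | 0.20 + 0.80 × 0.10 = 28% | 0.20 + 0.80 × 0.40 = 52% |

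At f = 0 there is no artefact.

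**Step 4. Scale of the denominator, also by assumption.** Section 1.2 cites post-transplant MRD- rates of 53% to 93%. If these held among the 45 evaluable patients of Section 10.2, MRD+ at Day +100 would number 45 × (1 - 0.93) = 3.15, about 3, to 45 × (1 - 0.53) = 21.15, about 21. One patient then carries 1/21 = 4.8 to 1/3 = 33.3 percentage points. That is the weight of any single patient in a small group, not an estimate of bias, and the assays behind the cited rates may differ from this one.

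**Step 5. The 1-year visit.** Both sources are scheduled, as at Day +100, so the comparison is matched. If the 1-year marrow is missed or inadequate, only blood remains and that patient has the same mismatch. Section 6.5.13 leaves a retest after an indeterminate result to the Investigator's discretion.

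**Step 6. With a same-source rule.** Patients who were negative in blood at Day +100 are not in the blood-to-blood denominator, so the term (1 - c) × f is zero by construction.

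**The case against.** The best answer is that this is detail awaiting a SAP. Section 10.4 sends the full analysis there, and a source rule may be in it. The text available for this review contains none, so the gap is in what is written so far. The objection limits the claim to that and does not close it.

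Second, the data to detect the problem will exist. Each source is assayed separately, the number of residual clonal cells is recorded (Section 9.3), and a marrow-blood comparison is planned. A 12-month marrow would expose a patient who looked negative in blood at 6 months. This stands for 6 months, if the marrow is obtained. It does not help at 24 months, when no marrow follows.

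Third, the endpoint is descriptive and secondary in a single-arm study. No test, sample size or PFS analysis depends on it. This stands in full.

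A reader might also infer something stronger from Sections 9.3 and 10.4.2: that MRD- always needs a negative result from both blood and marrow, so that nobody can be MRD- at 6 or 24 months and conversion there is 0% by construction. The documents do not support this. Section 6.5.13 confines the combining rule to visits with both sources, which implies that other visits are judged on the source taken. It also schedules the 6- and 24-month blood samples in order to follow change from MRD+ to MRD-, which that reading would make impossible.

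**Conclusion.** The point holds as a gap in the analysis rule. With single-source visits judged on the source taken, conversion at 6 and 24 months can include patients whose disease did not change, and the bias can only be upward.

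A reader might infer that the conversion rate is materially inflated. The documents do not show that: they give no marrow-only share, it could be zero, and the percentages in the working rest on assumed values. Nor is the 1-year comparison safe without qualification, since it is matched only for patients whose 1-year blood and marrow are both evaluable. The consequence is confined to a descriptive secondary endpoint, and the correction is worth making because it is cheap and can be fixed before results are seen.

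**What to change.** Add to Section 10.4.2 or the SAP that conversion is computed like for like:

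- **Blood to blood** at 6, 12 and 24 months, among patients who were MRD+ in blood at Day +100.
- **Composite to composite** at 1 year, among patients who were MRD+ in either source at Day +100 and have both sources evaluable at 1 year. A negative 1-year blood result without an evaluable marrow does not count as MRD-.
- **Patients positive only in marrow at Day +100** are not converters on a blood-only visit. List them separately.

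There is no need to make 1 year the main conversion analysis. That would be a preference, and the objective runs to 2 years.

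The cost is a few sentences, with no new samples or tests. The blood analysis has a smaller denominator, and there is no 24-month conversion figure for patients positive only in marrow.

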### **6.5.14 Radiologic Assessments**

Response assessments will be evaluated based on recent International Working Group consensus criteria Response Evaluation Criteria in Lymphoma (RECIL 2017) (Younes et al 2017), outlined in Appendix E and Appendix F.

Tumor assessments will be performed using radiologic imaging by CT scan with contrast covering neck, chest, abdomen, and pelvis and [F]2-fluoro-2-deoxy-D-glucose-positron emission tomography (FDG-PET) scan covering from base of skull to mid-thigh within 28 days before the first dose of study drug and as outlined in Appendix D. In certain cases, measurements may be performed on the CT component of a combined PET-CT image, provided that is of adequate resolution. In the latter instance, approval by the sponsor is required.

Magnetic resonance imaging (MRI) may be used for imaging assessments if a contrast CT scan is contraindicated or undesirable. In cases where MRI is desirable, the MRI must be obtained at baseline and at all subsequent response evaluations.

#### **CT/MRI measurements**

Assessment of tumor burden will use the sum of the longest diameters. In subjects with disseminated disease, a maximum of 3 target lesions should be selected to estimate tumor response.

Target lesions should be selected per the following:

- They should be selected from those of the largest size that can be measured reproducibly and preferably representing multiple sites and organs.
- Lymph nodes:
  - Lymph nodes can be considered target lesions if the lymph node longest diameter measures  $\geq 15$  mm.

- A lymph node measuring between 10 and 14 mm is considered abnormal but should not be selected as a target lesion.
- Lymph nodes measuring  $<10$  mm in diameter are considered normal and cannot be used as target lesions.
- In certain anatomical sites (inguinal, axillary, and portacaval), normal lymph nodes may exist in a narrow, elongated form, and such nodes should not be selected as target lesions if alternatives are available.
- Extranodal lesions can be selected as target lesions if they have a soft tissue component, based on their size and the ease of reproducibility of repeated measurements, with a minimum measurement of the longest diameter of  $\geq 15$  mm.
- Nontarget lesions:
  - All other lesions should be identified as nontarget lesions and should be recorded at baseline, without the need to measure them.
  - Nontarget lesions should be followed and reported as present, absent, or clear progression.

### **FDG-PET measurements**

Scoring is semi-quantitative using the Deauville 5-point scale (Deauville 5PS). It is a simple tool based on visual interpretation of [ $^{18}\text{F}$ ]2-fluoro-2-deoxy-D-glucose (FDG) uptake. It takes advantage of two reference points on the individual subject which have demonstrated relatively constant uptake on serial imaging. The two reference organs are the mediastinum and the liver. The scale ranges from 1 to 5, where 1 is “no FDG uptake” and 5 is “markedly increased FDG uptake”. Each FDG-avid (or previously FDG-avid) lesion is rated independently.

1. No uptake or no residual uptake (when used interim)
2. Slight uptake, but below blood pool (mediastinum)
3. Uptake above mediastinal, but below or equal to uptake in the liver
4. Uptake slightly to moderately higher than liver
5. Markedly increased uptake or any new lesion (on response evaluation)

## 7. DRUG FORMULATION, AVAILABILITY, ADMINISTRATION, AND TOXICITY INFORMATION

### 7.1 Acalabrutinib

| Investigational Product | Dosage Form and Strength | Manufacturer  |
|-------------------------|--------------------------|---------------|
| Acalabrutinib           | 129 mg tablets           | Acerta Pharma |

### 7.2 Acalabrutinib Treatment Duration

Acalabrutinib tablets will be self-administered BID approximately every 12 hours. The tablets should be swallowed intact with approximately 1 cup of water. Patients should not chew the tablets and should try to swallow tablets whole.

If a dose is missed, it can be taken up to 3 hours after the scheduled time with a return to the normal schedule with the next dose. If it has been >3 hours, the dose should not be taken and the patient should take the next dose at the scheduled time. The missed dose will not be made up and must be returned to the site at the next scheduled visit.

#### 7.2.1 Labeling, Packaging, and Supply of Acalabrutinib

The investigational product, acalabrutinib maleate tablet, is supplied as an orange film-coated tablet containing 129 mg of acalabrutinib maleate (equivalent to 100 mg of acalabrutinib) drug substance.

Each tablet also contains the following compendial inactive ingredients: mannitol, microcrystalline cellulose, low-substituted hydroxypropyl cellulose, and sodium stearyl fumarate. The tablet coating contains hypromellose, copovidone, titanium dioxide, polyethylene glycol, caprylic/capric triglyceride, yellow iron oxide, and red iron oxide.

Acalabrutinib maleate tablets are packed in white, high-density polyethylene (HDPE) bottles containing a silica gel desiccant and should be stored according to the storage conditions as indicated on the label. The recommended storage condition for acalabrutinib maleate tablets is below 30°C (86°F).

Study drug will arrive commercially labeled as CALQUENCE®. Innovations will affix labels reading “LYM 155 – For Investigational Use Only” before distribution.

### 7.3 Accountability for the Study Drug

The PI (or designee) is responsible for accountability of all used and unused study drug supplies at the site. Innovations representatives must be granted access on reasonable request to check drug storage, dispensing procedures, and accountability records.

All study drug inventories must be made available for inspection by Innovations or its representatives and regulatory agency inspectors upon request.

Throughout the study and at its completion, Innovations Drug Accountability Record Form(s) will be completed by the site and sent to the Innovations Regulatory Department. Study drug supplies must not be destroyed unless prior approval has been granted by Innovations. Please contact Innovations regarding disposal of any study drug.

